## Study Summary

Title	Penile Length Restoration in Men with Diabetes Mellitus, Type II
IRB Protocol Number	18-006696
Methodology	Controlled randomized study
Overall Study Duration	3 years
Subject Participation Duration	6 months
Objectives	Evaluate the efficacy of the RestoreX penile traction device in restoring length loss secondary to diabetes mellitus
Number of Subjects	120
Diagnosis and Main Inclusion Criteria	Men with diabetes mellitus, type II
Study Device	RestoreX®, penile traction therapy
Duration of Exposure	Subjects in Groups 1-3 will use device for 3 months for 30 minutes, twice daily. Subjects in Group 4 will be control and will not use the device.  After the randomized period, subjects using the device will switch to not using the device (Group 1), using the device once weekly x 30 minutes (Group 2), or continuing to use the device twice daily x 3 months (Group 3).
Reference therapy	The use of the device will be compared against a control group using no traction therapy. Individuals will also be compared to themselves to evaluate changes from baseline.
Statistical Methodology	Stratification of subjects prior to randomization to assure an equal representation based on baseline penile length. Statistical comparisons will be made comparing total penile length prior to and following therapy. Comparisons of subjective questionnaire responses will also be made between groups and at the various time points captured.

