## 2 Study Objectives

### 2.1 Primary Objective

1. The primary objective is to assess penile length pre and post completion of RestoreX® traction therapy compared to control groups (no treatment) of DM subjects.

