### 3.4 Consent and Enrollment

Patients wishing to enroll in the study will be given the opportunity to meet with the study coordinator to further review study details and formal consent.

Patients that would like additional time to consider their participation will be given other opportunities to meet with the study coordinator if desired. If the patient expresses interest in participating at any of these times, a formal consent will be reviewed (see **Attachment – Consent Form**).

At enrollment, all participants will be assigned a study identifier, with a master list maintained in a password protected database (Mayo server – RAVE database) linking the patient to the identifier. A total of 30 patients will be enrolled into each arm of the study for a total of 120 patients enrolled overall. It is estimated that up to 360 patients will need to be screened to enroll the 120 patients.

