#### 5.2 Statistical Analysis

Analyses will be performed using comparisons within patients of same baseline penile stretch length and between groupings of varying lengths. Comparison of penile length between traction and no traction will be made, as well as reviewing historical records to increase statistical power. Comparison of length from baseline to post-traction for individual participants will also be reviewed.

The data will also be analyzed in three ways: 1- with all patients included, regardless of their compliance to utilize the device for the recommended treatment time, 2- with patients excluded if they failed to achieve 90% compliance with the recommended duration of treatment, 3- with patients excluded if they failed to achieve 75% compliance with the recommended duration of treatment. Factors which will also be included to determine compliance will include frequency and duration of use and whether or not the device was used correctly (black rods buried, amount of time white line showing).

Comparisons will also be made on other subjective and objective variables obtained including number of adverse events, complications, subjective responses to questionnaires, or other information. All data will be normalized by baseline stretched penile length.

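### Before-after length comparisons in traction users sit beside the controlled comparison with nothing to say they are not efficacy evidence

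*Combined protocol and SAP*

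**What the plan says.** **Controlled comparison.** The plan contains one in three places. Section 2.1 sets out to "assess penile length pre and post completion of RestoreX® traction therapy compared to control groups (no treatment) of DM subjects". The Reference therapy row of the Study Summary sets the device against a control group without traction. Section 5.2 states: "Comparison of penile length between traction and no traction will be made, as well as reviewing historical records to increase statistical power".

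**Before-after comparison.** This also appears in three places.
- Study Summary, Statistical Methodology row: "Statistical comparisons will be made comparing total penile length prior to and following therapy". For length, this row names no other comparison; its only between-group comparison concerns questionnaire responses.
- Study Summary, Reference therapy row: "Individuals will also be compared to themselves to evaluate changes from baseline".
- Section 5.2, after the traction v no-traction sentence: "Comparison of length from baseline to post-traction for individual participants will also be reviewed". This refers to traction users and does not promise the same display for controls.

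**Ranking.** No section names a primary contrast, test, time point or significance level for length, and none says that the before-after results are descriptive.

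**Numbers.** Section 3.4: "A total of 30 patients will be enrolled into each arm of the study for a total of 120 patients enrolled overall". Study Summary: "Subjects in Groups 1-3 will use device for 3 months for 30 minutes, twice daily" and "Subjects in Group 4 will be control and will not use the device".

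**The concern.** A before-after test in treated men cannot separate a device effect from anything else that moves the measurement between visits. Such movement is plausible here. Section 4.4 has length measured by a clinical team member and specifies no stretching force, repeat measurement, constant measurer or blinding. Section 3.5 has the baseline taken by a urology provider and a Men's Health Nurse, so the measurer may differ between visits.

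Regression to the mean is less of a worry for the whole group, because entry does not depend on length. It can still move the baseline-length strata, and section 5.2 plans comparisons among men of the same baseline length.

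The allocation adds to the difficulty. Up to month 3, Groups 1-3 follow one regimen, so a pooled look has three times as many traction men as controls. The same drift is then much likelier to reach significance with traction than without. A reader shown both results could take that pattern as efficacy although the randomized difference shows none.

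**Working it through.** **Inputs from the documents.** 30 men per arm and four arms: 4 x 30 = 120, which matches the stated total. Groups 1-3 share a regimen to month 3: 3 x 30 = 90 traction, against 30 control. There is no power calculation to reproduce.

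**Assumptions, because the documents are silent.** Two-sided 5% tests; normally distributed changes with equal SD; no dropout; zero device effect; the same shift d (in SDs of change) in every arm; Groups 1-3 pooled.

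**Method.** For a paired t-test on n men, the noncentrality is d x sqrt(n). P_n is the chance of significant lengthening. The two groups are independent, so

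P(traction significant, control not) = P_90 x (1 - chance that control is significant in either direction).

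Example, d = 0.3: the noncentralities are 0.3 x sqrt(90) = 2.85 and 0.3 x sqrt(30) = 1.64, giving P_90 = 0.804 and P_30 = 0.355. The product is 0.804 x (1 - 0.355) = 0.52. At d = 0 it is 0.025 x (1 - 0.05) = 0.024.

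| Common shift (SD of change) | Traction significant, n=90 | Control significant (lengthening), n=30 | Traction significant, control not |
|---|---|---|---|
| 0 | 2.5% | 2.5% | 2.4% |
| 0.1 | 15% | 8% | 14% |
| 0.2 | 47% | 18% | 38% |
| 0.3 | 80% | 36% | 52% |
| 0.4 | 96% | 56% | 42% |
| 0.5 | 99.7% | 75% | 25% |
| 0.8 | 100% | 99% | 1% |

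The maximum lies at a shift of about 0.30. For large shifts both groups are significant and the contrast disappears.

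**Sensitivity.**
- One traction arm against control (30 v 30, the relevant layout at month 6, when regimens differ): the probability is P_30 x (1 - P_30), which cannot exceed 25%. It is 15, 23 and 25% at shifts of 0.2, 0.3 and 0.4.
- 15% dropout (76 v 25): 34, 51 and 48% at the same shifts.

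**Randomized comparison under the same conditions.** In a simulation of 50,000 trials per shift, the two-sample test of change (90 v 30) was significant in 4.8, 4.9, 5.1, 5.0 and 5.0% of trials at shifts of 0, 0.2, 0.3, 0.4 and 0.5. A common shift cancels in the difference between arms.

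**The case against.** A reader of the Statistical Methodology row alone might infer that the trial has no controlled analysis of length. The documents do not support that. The primary objective is controlled, section 5.2 puts traction v no traction ahead of the individual comparison, and both section 5.2 and the Reference therapy row introduce self-comparison with the word also.

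A reader might also infer that the plan intends to set a significant traction result against a non-significant control result. No section says so. Section 5.2 speaks of reviewing individual changes and names no test or efficacy criterion for them, and nowhere are Groups 1-3 expressly pooled. The pattern in the table is therefore a misreading that the plan leaves open, not an analysis that it prescribes.

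The safeguard is also real. In a simulation of the same null case, the misleading pattern coincided with a significant between-group difference favouring traction in only 2.3-2.6% of trials at shifts of 0.2-0.4 SD. In nearly all the rest, the planned randomized comparison would not have supported the device. Length is measured in every arm, so control drift can be seen.

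All of this stands, and it limits the point. It does not remove it: the summary calls the before-after comparison statistical, and no text ranks it below the randomized contrast. Even without a side-by-side display, a lone before-after p-value in traction users is not evidence that the device works.

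**Conclusion.** The concern holds as one of status, not of a missing control analysis. Uncontrolled before-after comparisons stand next to the randomized comparison, and nothing bars them from carrying the efficacy conclusion.

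The illustrated risk depends heavily on an unknown drift. Over shifts of 0.1-0.5 SD it runs from 14% up to 52% and back to 25%. It is only 2.4% with no drift and 1% at 0.8 SD. The figures of 38-52% at 0.2-0.4 SD surround the maximum and should not be read as the expected error rate. They also assume pooling that fits month 3 only; a single arm against control gives at most about 25%.

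The firmer result is the contrast in behaviour: under a common shift the before-after test loses its error control, while the randomized test stays at about 5%. The randomized test would not remove a bias that differs between arms, for instance from unblinded measurement; that is a separate matter. The sponsor should make the clarification, since it replaces an ambiguous and potentially biased basis for efficacy at no cost.

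**What to change.** In the Statistical Methodology row of the Study Summary and in section 5.2, state two things:

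1. The efficacy conclusion on penile length rests on the difference between the randomized traction and control groups, adjusted for baseline length (for example by analysis of covariance), reported with its confidence interval.
2. Within-person changes from baseline are descriptive. They are shown side by side for all four groups, control included, as means with confidence intervals, and are not used to claim efficacy.

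The self-comparison sentence in the Reference therapy row should point to the second statement.

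This is a free improvement: two sentences, no new data or visits, no change to any procedure, and no result lost. It also brings the summary into line with the primary objective in section 2.1.

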### 3.5 Study Schema

All patients will have been previously seen at Mayo Clinic for a condition of DM. Following enrollment, key factors relating to their underlying condition will be abstracted from the chart by a study coordinator, including age, duration of disease (if known), number of DM medications, use of insulin, most recent fasting glucose and HbA1c, creatinine, and testosterone, HOMA1-IR, HOMA2-IR, and BMI. If any of these variables are not available, no additional attempts will be made to retrieve the information.

At the initial appointment, patients will also undergo a penile length assessment by a urology provider and Men's Health Nurse and receive questionnaires (IIEF-15 and disease specific history)

Once consent and study assessments are completed, the patients will be randomized into one of four groups:

1. PTT for 30 min 2x/day x 3 months, followed by no treatment x 3 months
2. PTT for 30 min 2x/day x 3 months, followed by once weekly (30 minutes) x 3 months
3. PTT for 30 min 2x/day x 6 months
4. Control (no treatment)

Patients in the treatment arm will record a daily journal of their usage of the device. Patients will then begin using the device as instructed for the times appropriate to their group.

After 3 months of using the device (+1.5 months permitted), patients will return for subsequent assessments (see below) and a follow-up questionnaire. At this time, patients will be encouraged to report any adverse events. They will also be requested to bring their device back to the clinic to review proper usage and any questions on the device. After completion of the subsequent assessments, patients will begin the second phase of the trial.

After 6 months (+ 1.5 months permitted) patients will return to the clinic to undergo final assessments, which are identical to the 3-month assessments.

Since participants are being asked to travel to Mayo Clinic for subsequent assessments, we will provide a remuneration amount of up to \$600. The purpose is to assist participants in their travel to and from Mayo Clinic. Those that provide consent will be provided \$100 after their baseline assessment. After their second and third visits (3 and 6-months, respectively), they will receive \$250 for a possible total of \$600.

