### 4.2 3 Month Visit

- Penile length assessment
- Questionnaires
  - 3 month
  - IIEF-15
- Device usage diary retrieved from treatment group
- Device usage diary given to all participants

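### The three analysis sets are unranked, and the 90% and 75% compliance sets can drop men only from the device groups, so comparing those sets with control can be biased

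*Combined protocol and SAP*

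**What the plan says.** Section 5.2 states: "The data will also be analyzed in three ways: 1- with all patients included", whatever their compliance. The second set is defined "with patients excluded if they failed to achieve 90% compliance with the recommended duration of treatment", and the third repeats this at 75%. The numbers 1 to 3 are list labels. Neither section 5.2, the Study Summary nor the objectives in section 2 calls any of the three primary, supportive or sensitivity.

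On how compliance is judged, section 5.2 says "Factors which will also be included to determine compliance will include frequency and duration of use", and adds correct use of the device. It gives no rule for combining these items.

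On the control group, the Study Summary says "Subjects in Group 4 will be control and will not use the device". The primary objective (section 2.1) is a comparison with untreated controls, and section 5.2 says "Comparison of penile length between traction and no traction will be made" shortly before it introduces the three sets.

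On the source of compliance data, section 3.5 says "Patients in the treatment arm will record a daily journal of their usage of the device", and section 4.2 lists "Device usage diary retrieved from treatment group" at month 3.

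**The concern.** There are two linked problems.

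First, the lack of ranking. If the three analyses disagree, a reader cannot tell which one answers the primary objective. The choice could be made after the results are known.

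Second, one-sided selection. A control has no recommended use, so he cannot fall short of it. The restricted sets therefore keep all controls but only the more adherent device users. Randomization no longer protects that comparison. If adherent men would have shown a different length change anyway, the difference is credited to, or held against, the device.

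A further gap concerns timing. The recommended duration is not tied to a visit. Groups 1-3 share one schedule to month 3 and then diverge; Group 3, for example, is assigned "PTT for 30 min 2x/day x 6 months". If the duration means the whole assigned course, a Group 3 man could be dropped from a month-3 comparison because of what he did after month 3. The same would hold for Group 2, which has its own schedule after month 3.

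**Working it through.** **Can the rule remove a control?** Compliance is built from frequency, duration and correctness of device use (5.2). Group 4 uses no device (Study Summary, 3.5). Section 4.2 issues a diary to all participants at month 3, and the table in 4.5 does not restrict diaries by group, but a diary gives a control no target to miss. The rule can remove men only from Groups 1-3.

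**Are the restricted sets confined to within-patient change?** Section 5.2 plans both a traction v no-traction comparison and a baseline-to-post-traction comparison, then applies the three sets to the data without limit. Use against control is not stated outright, but it is not ruled out.

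**Inputs from the documents.** Four arms of 30 (3.4): 4 × 30 = 120 in total, 3 × 30 = 90 device men and 30 controls. The plan gives no alpha, power, effect size, SD or expected compliance, so it has no figure of its own to reproduce.

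**Assumed inputs.** No device effect; two-sided 0.05; pooled-variance t-test; outcome SD of 1; complete outcome data; adherence and outcome bivariate normal with correlation r in device users. Two retention scenarios:
- A: 85% of device men reach 75% compliance and 70% reach 90% (77 and 63 of 90; 26 and 21 of 30).
- B: 60% and 40% (54 and 36 of 90; 18 and 12 of 30).

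**Size of the bias.** If a share k of device men is kept by adherence and all controls are kept, the expected false difference is r × φ(z)/k SD, where z is the normal cut-off with share k above it. For k = 0.40, z = 0.253, φ(z) = 0.386 and 0.386/0.40 = 0.966. At r = 0.3 the bias is 0.3 × 0.966 = 0.29 SD; at r = 0.1 it is 0.10 SD. Simulation with exact counts (200,000 trials per setting, 90 v 30) gives:

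| r | 85% kept | 70% kept | 60% kept | 40% kept |
|---|---|---|---|---|
| 0.1 | 0.026 SD | 0.049 SD | 0.063 SD | 0.095 SD |
| 0.3 | 0.078 SD | 0.147 SD | 0.191 SD | 0.287 SD |

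There is no bias at r = 0. The all-patients analysis has none at any r.

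**Chance that at least one of the three analyses is falsely significant** (scenario A, scenario B). A single test gives 2.5% in favour of the device and 5% in either direction.

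| r | Favours device, 90 v 30 | Favours device, 30 v 30 | Either direction, 90 v 30 |
|---|---|---|---|
| 0 | 3.4%, 4.1% | 3.8%, 4.6% | 6.8%, 8.2% |
| 0.1 | 4.6%, 7.2% | 4.7%, 6.7% | 7.4%, 10.1% |
| 0.3 | 10.3%, 22.8% | 7.9%, 14.9% | 12.7%, 25.3% |
| -0.3 | 2.5%, 2.5% | 2.6%, 2.6% | 13%, 25% |

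The row for r = 0 shows the effect of the missing ranking alone. The other rows add the selection. At -0.3 the bias runs against the device, and the two-directional figure mirrors that at +0.3.

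**The case against.** The strongest reply is that the plan never says the restricted sets will be compared with control. The sentence on within-patient change comes directly before the three sets, so they may be meant only for that. An all-patients analysis is planned and listed first, and adding compliance thresholds beside it is ordinary sensitivity practice. On this view only a label is missing.

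The figures can also be challenged. The lack of ranking alone moves the chance of falsely favouring the device only from 2.5% to about 3.4% to 4.1%. The larger numbers need an assumed correlation of 0.3, for which the documents give no evidence. The simulation also leaves out the normalization by baseline length that section 5.2 mentions. Finally, diaries are collected at month 3 and again at month 6, so compliance by period is already feasible, and the Group 3 example depends on one reading of the recommended duration.

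Much of this stands as a limit on strength. The bias is conditional, its size is not known, and the all-patients analysis is not affected by the selection. It does not remove the point. The wording covers the data without restriction, the primary objective is the comparison with control, and no sentence gives the all-patients analysis priority. That compliance by period could be computed does not mean that the plan says it will be.

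**Conclusion.** The concern holds. No analysis is designated as primary, and the compliance rule can exclude men only from Groups 1-3. If the restricted sets are compared with control, the result is biased whenever adherence is related to length change for reasons other than the device.

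The documents determine neither direction nor size. Under the assumptions above, the false difference at 90 v 30 is 0.03 to 0.10 SD at a correlation of 0.1 and 0.08 to 0.29 SD at 0.3. This is a point that should be corrected rather than a fatal flaw, because a suitable analysis is already in the plan and lacks only priority.

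**What to change.** In section 5.2:

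1. State that the analysis of all randomized patients, as assigned, is the sole basis for the primary comparison with control.
2. Label the 90% and 75% sets supportive, and say that they are not tests of efficacy against control.
3. For the month-3 comparison, compute compliance in Groups 1-3 from the month 0-3 diary already retrieved at that visit. State the period that applies to any month-6 use of the sets.
4. Fix how frequency, duration and correct use combine into the compliance percentage before length outcomes are seen.

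The cost is a few sentences, with no added visit, patient or measurement. The price is that compliance-restricted results can no longer carry an efficacy claim. The primary visit, the pooling of Groups 1-3 and the handling of missing lengths must still be settled separately. Whether the diary records the correct-use items cannot be checked, because that attachment is not in the documents.

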## 6 Safety and Adverse Events

### Definition of Adverse Event

Unanticipated Problems Involving Risk to Subjects or Others (UPIRTSO) - any unanticipated problem or adverse event that meets the following three criteria:

Serious: Serious problems or events that results in significant harm, (which may be physical, psychological, financial, social, economic, or legal) or increased risk for the subject or others (including individuals who are not research subjects). These include: (1) death; (2) life threatening adverse experience; (3) hospitalization - inpatient, new, or prolonged; (4) disability/incapacity - persistent or significant; (5) breach of confidentiality and (6) other problems, events, or new information (i.e. publications, interim findings, product labeling change) that in the opinion of the local investigator may adversely affect the rights, safety, or welfare of the subjects or others, or substantially compromise the research data, AND

Unanticipated: (i.e. unexpected) problems or events are those that are not already described as potential risks in the protocol, consent document, not listed in the Investigator's Brochure, or not part of an underlying disease. A problem or event is "unanticipated" when it was unforeseeable at the time of its occurrence. A problem or event is "unanticipated" when it occurs at an increased frequency or at an increased severity than expected, AND

Related: A problem or event is "related" if it is possibly related to the research procedures.

Adverse Event - an untoward or undesirable experience associated with the use of a medical product (i.e. drug, device, biologic) in a patient or research subject.

Serious Adverse Event - adverse events are classified as serious or non-serious. Serious problems/events can be well defined and include:

- Death
- Life threatening adverse experience
- Hospitalization
- Inpatient, new, or prolonged; disability/incapacity
- And/or per protocol may be problems/events that in the opinion of the sponsor-investigator may have adversely affected the rights, safety, or welfare of the subjects or others, or substantially compromised the research data.

All AEs that do not meet any of the criteria for serious, should be regarded as non-serious AEs.

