### 2.2 Secondary Objectives

1. Compare patient compliance with traction device.
2. Compare patient reported satisfaction with use of traction device.
3. Evaluate any adverse events (AEs) with use of RestoreX® for penile lengthening.
4. Compare the rate of Peyronie's disease development among groups
5. Compare patient satisfaction scores including satisfaction with overall penile length.
6. Evaluate and compare patient erectile function among groups
7. Review associations between DM factors and standardized questionnaires and outcomes

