## **6.2 Preexisting Condition**

A preexisting condition is one that is present at the start of the study. A preexisting condition should be recorded as an adverse event if the frequency, intensity, or the character of the condition worsens during the study period.

At screening, any clinically significant abnormality should be recorded as a preexisting condition. At the end of the study, any new clinically significant findings/abnormalities that meet the definition of an adverse event must also be recorded and documented as an adverse event.

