## **6.5 Recording of Adverse Events**

The study team will seek information on adverse events by specific questioning between baseline and the follow-up visits. Information on all adverse events will be recorded immediately in the adverse event section of the specific questionnaire as well as in an adverse event form (see Attachment – Adverse Event Form).

All adverse events occurring during the study period will be recorded. The clinical course will be followed until resolution, stabilization, or until it has been ultimately determined that the study treatment or participation is not the probable cause. Serious adverse events that are still ongoing at the end of the study period will be followed up, to determine the final outcome. Any serious adverse event that occurs after the study period and is considered to be at least possibly related to the study treatment or study participation will be recorded and reported immediately.

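### The adverse-event definition is tied to product use and not reconciled with the arm-neutral recording rules, so counts in the untreated group may be incomplete and a traction versus no-traction comparison biased

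*Combined protocol and SAP*

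**What the plan says.** Section 6 (Definition of Adverse Event) defines an adverse event as "an untoward or undesirable experience associated with the use of a medical product (i.e. drug, device, biologic) in a patient or research subject". Serious events are a subdivision of adverse events, so they inherit the product link.

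The Study Summary states that "Subjects in Group 4 will be control and will not use the device", and section 3.5 lists that group as receiving no treatment. Section 5.2 plans that "Comparisons will also be made on other subjective and objective variables obtained including number of adverse events, complications" will be examined, without naming the groups, the unit (events or participants) or a test. The safety item in section 2.2 is worded for exposure: "Evaluate any adverse events (AEs) with use of RestoreX® for penile lengthening".

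The recording rules read differently from the definition. Section 6.5 says "The study team will seek information on adverse events by specific questioning between baseline and the follow-up visits" and "All adverse events occurring during the study period will be recorded", with no restriction by arm. Section 6.2 says "A preexisting condition should be recorded as an adverse event if the frequency, intensity, or the character of the condition worsens during the study period", with no product condition. The adverse event form in section 6.6.1 carries relationship to the study as a field of its own.

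**The concern.** If product association is a condition of entry, whether an event is counted depends partly on the arm. A device user's new infection, skin complaint or hospital admission can be linked to the device or to another product. A control's can be linked only to another product. Staff who apply the definition closely would then leave out some control events whose counterparts in Groups 1 to 3 are recorded.

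At stake is the interpretation of the safety comparison. With fewer control events counted, ordinary events in men with diabetes could look like device harm. Events never written down for controls may be impossible to recover at analysis. This affects a secondary outcome; the primary length comparison is untouched.

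**Working it through.** The plan gives no adverse-event rate for controls and no alpha or power for this comparison, so there is no stated figure to reproduce. The check is a reading of the text, followed by an illustration on assumed rates.

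**Text, side by side**

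1. The definition requires association with a medical product. It does not say the study device; any drug, device or biologic will do.
2. Section 6.5 records all adverse events, but that term takes its meaning from the definition. The rule is neutral between arms, yet still passes through the product condition.
3. Section 6.2 splits. Worsening of a preexisting condition counts unconditionally. A new finding at the end of the study counts only if it meets the definition, which leads back to step 1.
4. Sections 6.5 and 6.6.1 judge relatedness after recording. That step is largely redundant if association is already required for entry, which suggests that the definition is the outlier.
5. The word *associated* can be read two ways. If causal, an ordinary diabetes-related admission is not an adverse event in either arm, but a doubtful case in a device user can still be attributed to the device. If it means only occurring during use, every event in a current device user qualifies, while a control's qualifies only if he uses some other product. On either reading a device user has one route that a control lacks.

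**Illustration**

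Input from section 3.4: "A total of 30 patients will be enrolled into each arm of the study for a total of 120 patients enrolled overall". That gives 4 × 30 = 120, with 3 × 30 = 90 on traction and 30 controls.

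Assumptions, none from the documents: the same true event rate b in both groups, all device-user events counted, a share c of control events counted, one event per participant at most, and a two-sided Fisher exact test at 0.05.

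Expected counts are 90b and 30bc. The spurious difference in rates is b − bc = b(1 − c). The last column is the exact probability of p ≤ 0.05, summed over both binomial distributions.

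| b | c | Expected counts, traction v control | Spurious difference | Chance of p ≤ 0.05 |
|---|---|---|---|---|
| 5% | 100% | 4.5 v 1.5 | 0 | 2.4% |
| 5% | 50% | 4.5 v 0.75 | 2.5 points | 0.4% |
| 5% | 0% | 4.5 v 0 | 5 points | 0.2% |
| 10% | 100% | 9 v 3 | 0 | 3.0% |
| 10% | 50% | 9 v 1.5 | 5 points | 4.4% |
| 10% | 0% | 9 v 0 | 10 points | 18.6% |
| 20% | 100% | 18 v 6 | 0 | 3.7% |
| 20% | 50% | 18 v 3 | 10 points | 18.4% |
| 20% | 0% | 18 v 0 | 20 points | 96.2% |
| 30% | 100% | 27 v 9 | 0 | 3.9% |
| 30% | 50% | 27 v 4.5 | 15 points | 34.1% |
| 30% | 0% | 27 v 0 | 30 points | about 100% |

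The c = 0% rows are an extreme, and p values there are sensitive to a single control event. Taking rates of 10%, 15% and 20% in 90 device users (9, 13.5 rounded to 14, and 18 events):

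| Control events recorded | 9/90 | 14/90 | 18/90 |
|---|---|---|---|
| 0/30 | p = 0.110 | 0.020 | 0.006 |
| 1/30 | 0.448 | 0.112 | 0.040 |
| 2/30 | 0.729 | 0.352 | 0.154 |

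**The case against.** A reader might infer that controls cannot have an adverse event at all, so that the comparison is tilted by definition. The text does not support that. The definition names any medical product, all participants have type 2 diabetes, and diabetes medication and insulin use are abstracted for everyone (sections 3.5 and 4.1), so control events linked to other products qualify. An all-versus-none contrast would need a loose reading of *associated* for Groups 1 to 3 and a strict, study-device-only reading for Group 4. The plan sets no such rule.

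The operative rules are also largely neutral. Questioning and recording in section 6.5 are not limited to device users. The 3- and 6-month questionnaires in section 4.5 are scheduled without regard to arm, and the preexisting-condition rule would catch much of the background in this population. The questionnaires and the Adverse Event Form are attachments that are not available here, so it cannot be said that controls are not asked. Erectile function and Peyronie's disease are compared among groups whatever the adverse-event definition says. All of this stands, and it limits the claim to a possible bias.

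Section 5.2 does not name the groups for the adverse-event comparison. Traction versus no traction is the natural reading, because the same section names that contrast for length, but it remains an inference.

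Two further inferences should not be drawn. One is that the five-patient halt in section 6.6.2 is compromised: the rule names no arm, and leaving out control events would not hide an event in a device user. The other is that the control arm was included to show background event rates: the Study Summary and section 2.1 present it as the comparator for length.

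What the objection does not remove is the extra route to being counted that a device user has, or the path by which new findings return to the product-linked wording.

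**Conclusion.** The concern holds as an unreconciled definition with a possible ascertainment bias. The definition in section 6 does not fit the recording rules in sections 6.2 and 6.5 or the separate relatedness field in section 6.6.1, and the plan does not say how it applies to untreated men. A traction versus no-traction comparison of event numbers may be biased, probably against the device, since the likely error is under-counting in controls.

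The size cannot be derived from the documents. It depends on the background rate and on how staff apply the definition, and neither is given. On the assumptions above it runs from negligible (all control events counted, or a low background rate) to large (none counted at a background rate of 20% or more). The middle case, half counted at 10%, barely moves the chance of a significant result (4.4% against 3.0% with full recording), though the estimated difference is still off by 5 points. The change is worth making because it is cheap and concerns a rule the plan states.

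**What to change.** - Replace the definition in section 6 with: any untoward medical occurrence in a randomized participant, in any of the four groups, during the reporting period of section 6.1, whether or not related to the device.
- Record relatedness only in the existing field of the adverse event form.
- State in section 6.5 that the adverse-event questions at months 3 and 6 are the same in all four groups.
- State in section 5.2 that device-site events (erythema, cold glans, discomfort) are reported descriptively for device users, and that the other events are compared between groups.

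The cost is a few sentences of text and a few more forms for Group 4. No new visits are needed. With full recording in both arms, the expected spurious difference in the illustration is zero and the chance of a false significant result is 2.4% to 3.9% for assumed rates of 5% to 30%.
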